### **3.8 Recruitment**

We will recruit staff delivering Verbal Health Literacy training during a three month period in 2024.

IRAS 336469

V2.0 13052024

We will recruit service users from two services, one within Derbyshire Community Health Services NHS Trust and one within the Local Authority. Service user recruitment is likely to take place over a six month period to recruit the minimum required sample. This is because both services run on a rolling basis. That is week 1 for one person could be week 6 for another.

We will recruit service users who enrol on the 12 week weight management programme and 6 week pulmonary rehabilitation programme after staff have (or have not) attended the Verbal Health Literacy training.

That is:

- Public Health Intervention Advisors and service users from the Live Life Better Derbyshire tier two weight management service.
- Physiotherapists, specialist nurses and service users from the Derbyshire Community Health Services (DCHS) pulmonary rehabilitation service.

Recruitment will commence once HRA and NHS ethics approval is obtained. Written informed consent will be gained for all participants in the study.

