### 3.9.2. Service users' individual outcomes

#### LLBD Weight Management Programme

Between 15-25 people attend each 12 week rolling LLBD weight management programme. 33 programmes are likely to be ongoing between the three month study period in 2024, with a minimum and maximum of 495 and 825 service users joining in total. All service users starting the programmes during the period of the study will be invited to take part when they sign up. We estimate there will be approximately 660 attendees to the LLBD weight management programme. With a response rate of 50% to our request to participate in the evaluation, we expect there to be weight, health and wellbeing and Health Literacy scores at three time points for approximately 330 service users. Approximately 160 service users will be in groups led by trained and 160 in groups led by untrained staff. We expect to see a reduction in weight, an improvement in clinical outcomes and an improvement in wellbeing between baseline and 12 weeks and baseline and 26 weeks for both groups. We expect the changes to be larger in the trained group versus the untrained group. We expect there to be an improvement in Health Literacy domain scores between baseline and 12 weeks (the end of the program) for the trained group and no change for the untrained group.

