#### DCHS Pulmonary Rehabilitation Programme

Between 8-12 people attend the six week rolling programme across 6 venues. If we do two cohorts, there will be a minimum of 96 and a maximum of 144 service users

IRAS 336469

V2.0 13052024

joining the programme between the three month study period in 2024, and who will be invited to take part. With a response rate of 50% to our request to participate in the evaluation, we expect there to be clinical, health and wellbeing and Health Literacy scores at two points of time for approximately 72 service users. We expect to see improvement in the CRDQ and other secondary outcomes after attending the programme. We expect there to be an improvement in Health Literacy domain scores between baseline and 6 weeks after the end of the programme.

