## **6.Timescales**

(Ethics outcome dependent)-

June- July 2024 - Recruitment of staff participants and pre intervention staff observations.

July- August 2024 - Delivery of training package and pre and immediately post intervention staff questionnaires.

July – November 2024 – Recruitment of service users and baseline outcome measures and Health Literacy Questionnaire data collection.

August– February 2025 – Service user post intervention outcome measures and Health Literacy Questionnaire data collection.

September – October 2024 – Two month follow up staff questionnaires.

October – November 2024 – Post intervention staff observations and/or recording of consultations.

November - January 2025 – Staff focus group interviews.

August 2024– March 2025 - Data analysis.

January – March 2025 – Write report/disseminate.

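### Service-user recruitment is given three unreconciled lengths (six months, three months, July to November 2024), and the expected sample sizes rest on the shortest

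*Combined protocol and SAP*

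**What the plan says.** The protocol describes the service-user recruitment window in three places.

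- **Section 3.8 (Recruitment):** "Service user recruitment is likely to take place over a six month period to recruit the minimum required sample". The size of that minimum is not given. The three-month period that opens the same section concerns staff. Section 3.8 also says that service users are those who enrol after staff have, or have not, been trained.
- **Section 3.9.2 (individual outcomes):** for weight management, "33 programmes are likely to be ongoing between the three month study period in 2024, with a minimum and maximum of 495 and 825" joiners, taken as about 660. A 50% response gives about 330, or roughly 160 per group. For pulmonary rehabilitation, two cohorts give 96 to 144 people "joining the programme between the three month study period in 2024, and who will be invited to take part", and a 50% response is said to give about 72.
- **Section 6 (Timescales, dependent on the ethics outcome):** "July – November 2024 – Recruitment of service users and baseline outcome measures". Training is scheduled for July to August 2024, and service-user outcome collection ends in February 2025.

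The only numerical sample requirement is in section 3.9.3: 252 per group for 4.7 kg v 4.3 kg, SD 1.6, 80% power and 5% significance. It stands under service-level outcomes.

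**The concern.** The window determines who is invited, when recruitment closes and how many people enter the individual-level analyses, including the trained v untrained regression in section 3.10.4. The eligibility criteria in section 3.8.1 refer to an intervention period and a data collection period without giving either a length, so they do not settle it.

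Section 3.8 treats six months as the likely time needed to reach a minimum, while section 3.9.2 projects the sample from half that time. Someone working from section 3.9.2 expects about 160 per group, well short of 252. Someone working from section 3.8 or section 6 expects more. Because the minimum has no value, neither reader can tell when recruitment is complete.

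**Working it through.** **1. Reproduce the stated numbers (three months).**

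- Weight management: 33 × 15 = 495; 33 × 25 = 825; midpoint 660. 660 × 0.5 = 330, and 330 / 2 = 165 per group (the plan says about 160).
- Pulmonary rehabilitation: 6 venues × 2 cohorts × 8 = 96, and × 12 = 144. At 50% this is 48 to 72, midpoint 60. The stated 72 is half of the maximum.

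**2. Reproduce the required size.** n per group = 2 × (1.96 + 0.8416)² × (1.6 / 0.4)² = 2 × 7.849 × 16 = 251.2, rounded up to 252. A two-sided 5% test matches the plan's figure.

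**3. Scale to the other windows.** Assumptions, not all stated in the plan: constant accrual, 50% response, equal groups, no loss to follow-up, no clustering by advisor. Consenting per group = 165 × months / 3. Power = Φ(0.25 × √(n/2) − 1.96), with 0.25 = 0.4 / 1.6.

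| Window | Weight service, per group (range from 495 to 825) | Power at midpoint | Pulmonary rehabilitation, consenting (midpoint) |
|---|---|---|---|
| 3 months (3.9.2) | 165 (124–206) | 62% | 48–72 (60) |
| 5 months (section 6) | 275 (206–344) | 83% | 80–120 (100) |
| 6 months (3.8) | 330 (248–413) | 89% | 96–144 (120) |

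The 330 in the last row is consenting people per group. It differs from the 330 consenting in total in section 3.9.2, and from the 330 per group who can be invited in section 3.9.3.

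Time to 252 consenting per group: 504 / 330 × 3 = 4.6 months at midpoint attendance; 3.7 months at the highest and 6.1 at the lowest.

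**4. Apply the training dates.** The trained group can accrue only after training. If all training finished at the end of August, a July to November window would leave September to November, three months, for the trained group: 165 × 3 / 3 = 165. With 275 untrained over five months, the standard error is 1.6 × √(1/165 + 1/275) = 0.158, and 0.4 / 0.158 − 1.96 = 0.58, giving about 72% power. If the untrained group is limited to the same three months, power returns to 62%.

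**5. Apply the end of outcome collection (end of February 2025).** A starter on 30 November reaches 12 weeks on 22 February, which fits. A starter on 31 December reaches 12 weeks on 25 March, which does not. Counting 26 weeks (182 days) back from 28 February 2025 gives 30 August 2024, so later starters cannot supply a 26-week weight within the timetable. Section 3.9.2 nevertheless expects scores at three time points for about 330 people.

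**The case against.** The strongest reply is that no rule is broken. Section 3.8 says only that six months is likely, section 6 is conditional on ethics approval, and section 3.9.2 is a projection that invites everyone starting during the study. The 330 and 72 are right for the window they name. A longer window brings in more people, so no analysis becomes invalid. All of that stands.

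It also disposes of a tempting stronger reading: that 330 and 72 contradict the plan's own recruitment rule by a factor of 1.7 to 2. That factor is merely 5/3 to 6/3, a ratio of durations under constant accrual. No section attaches a participant number to five or six months. For pulmonary rehabilitation the factor does not hold even on those terms: 72 already uses maximum attendance, so midpoint accrual gives 100 / 72 = 1.4 to 120 / 72 = 1.7.

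A second reply is that the three months may mean September to November, once training is finished. This is plausible, but the plan does not say so, section 6 starts service-user recruitment in July, and section 3.8 still says six months.

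A third is that 252 belongs to the aggregate comparison, which needs no individual consent. Its placement supports this, yet section 3.9.3 also speaks of inviting and recruiting people to reach 252. Its status is unclear, so the power figures above show what is at stake and do not establish a shortfall.

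**Conclusion.** The inconsistency is real: three windows for one quantity, no reconciliation, expected numbers built on the shortest, and a minimum sample without a value. On the assumptions in step 3, the choice moves the weight comparison from 62% power (three months) to 83% or 89% (five or six months), across the 80% used in section 3.9.3.

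A reader might infer that adopting a longer window secures the sample. The documents do not support that. At the lowest attendance, five months gives 206 and six months 248 per group, both below 252. Training dates may cut full trained-group accrual within July to November to about three months. The power figures also ignore loss and the clustering of service users within four trained and four untrained advisors. Nor can it be said that stopping at three months halves a required sample, because section 3.8 never states one.

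This is a consistency defect that should be corrected, with consequences for the expected numbers and the 26-week data.

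**What to change.** - State one service-user recruitment window, with dates, in sections 3.8, 3.9.2 and 6.
- Recompute the expected numbers for both services on that window. State the accrual assumption, give the range as well as a midpoint, and put pulmonary rehabilitation on the same midpoint basis as weight management.
- Count trained-group accrual only from the end of training, and say whether the untrained group is counted over the same dates.
- Say which number is the minimum sample in section 3.8, and whether 252 per group applies to consented individuals or only to the aggregate data.
- Check the window against February 2025. Either extend the collection date so that later starters can reach 26 weeks, or restate how many people are expected to have all three time points.

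The core cost is wording and arithmetic, with no enrolment beyond what sections 3.8 and 6 already foresee. Extending outcome collection would lengthen the timetable. Some restated figures may be less favourable than the present ones.

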### **3.8.1 Inclusion and exclusion criteria**

Inclusion criteria:

- Public Health Intervention Advisors delivering the tier 2 weight management programme across Derbyshire.
- Physiotherapists and specialist nurses involved in the assessment of patients and delivery of the six week DCHS NHS pulmonary rehabilitation programme.
- Adults aged 18 or over who start the rolling 12 week tier two weight management programme during the intervention period.
- Adults aged 18 or over, with Chronic Obstructive Pulmonary Disease, who are being assessed for and undertaking the six week pulmonary rehabilitation programme during the study intervention period.

- For the staff questionnaire only - Healthcare staff from other services that attend Verbal Health Literacy training, during the study period in 2024, will also be eligible.

Exclusion criteria:

- Service users attending the two service programmes outside of the data collection period.
- Other pulmonary rehabilitation staff. i.e. staff who are not physiotherapists or specialist nurses.

### **3.8.2 Process of recruitment**

Recruitment of staff will be carried out with the advice and assistance of the service leads. The study will be presented to each of the participating services by the lead researcher prior to recruitment commencing. An email invitation will be sent to all staff that deliver the programme in the two services via the service leads in the first instance. The email will include the study's participant information sheet. This information will include the lead researcher's contact details. This is so those staff who receive the Verbal Health Literacy training can get in touch should they be interested in taking part in the observations and focus groups or if any staff wish to discuss the project further.

In addition, all staff across DCHS and DCC that receive the Verbal Health Literacy training during the period of the study will be invited to participate via the pre and post training questionnaires. Participant information will be included with the questionnaires. Staff will be able to consent to their data being used for the research at the start of the questionnaire.

All service users that are referred or self-refer into the programmes during the period of the study, after staff have (or have not) been trained, will be invited to take part. Potential service user participants will be identified and approached by a member of their direct care team in the first instance. Because both programmes are rolling programmes, this means service users start their programmes at different times. Also, both services run across a number of different venues in Derbyshire. This

means it will be very difficult for the lead researcher to obtain face to face consent from service users. For this reason a number of different options for recruitment and consent will be used.

- A link to the study information and consent form will be included in the programme enrolment email that the services send out. Potential participants will be able to read this, contact the researcher for more information if they wish, and complete the consent form electronically if they would like to take part. This information and consent form will be delivered via The University of Sheffield information governance approved online survey platform, Qualtrics (Qualtrics.com).
- Those service users who cannot or do not wish to correspond via email will be given the one page project summary information sheet by the member of staff that enrolls them on the programme. The member of staff will ask the service user if their contact details can be shared with the lead researcher. The lead researcher will then contact potential service user participants by their preferred mode of contact (telephone or email) to invite them to take part. They will include the full participant information sheet with this correspondence (via email, post or verbally).
- Alternatively service users may contact the researcher themselves using the contact information on the summary information sheet.

A project information audio/video will be made available to all service users who are interested in taking part. This will be an alternative to the written information. Informed consent will be gained from all participants, electronically, over the telephone or by post in some instances where this is the participants preference. Prior to collecting or using any of their individual level data.

### **3.9 Sampling strategy and sample size**

#### **3.9.1. Staff**

There are currently eight staff that deliver the weight management programme. There are currently six physiotherapists and two specialist nurses who deliver the

pulmonary rehabilitation programme. Four out of the eight weight management programme staff will receive the Verbal Health Literacy training. Six physiotherapists and two specialist nurses from the pulmonary rehabilitation programme will receive the training. All staff from the two participating services who receive the training, n=12, and from the wider services who complete the training during the study period, will be asked to complete the three questionnaires.

All trained staff, from each of the two services (n=12) where possible, will be observed pre and post the intervention and be part of the focus groups.

### 3.9.2. Service users' individual outcomes

#### LLBD Weight Management Programme

Between 15-25 people attend each 12 week rolling LLBD weight management programme. 33 programmes are likely to be ongoing between the three month study period in 2024, with a minimum and maximum of 495 and 825 service users joining in total. All service users starting the programmes during the period of the study will be invited to take part when they sign up. We estimate there will be approximately 660 attendees to the LLBD weight management programme. With a response rate of 50% to our request to participate in the evaluation, we expect there to be weight, health and wellbeing and Health Literacy scores at three time points for approximately 330 service users. Approximately 160 service users will be in groups led by trained and 160 in groups led by untrained staff. We expect to see a reduction in weight, an improvement in clinical outcomes and an improvement in wellbeing between baseline and 12 weeks and baseline and 26 weeks for both groups. We expect the changes to be larger in the trained group versus the untrained group. We expect there to be an improvement in Health Literacy domain scores between baseline and 12 weeks (the end of the program) for the trained group and no change for the untrained group.

#### DCHS Pulmonary Rehabilitation Programme

Between 8-12 people attend the six week rolling programme across 6 venues. If we do two cohorts, there will be a minimum of 96 and a maximum of 144 service users

IRAS 336469

V2.0 13052024

joining the programme between the three month study period in 2024, and who will be invited to take part. With a response rate of 50% to our request to participate in the evaluation, we expect there to be clinical, health and wellbeing and Health Literacy scores at two points of time for approximately 72 service users. We expect to see improvement in the CRDQ and other secondary outcomes after attending the programme. We expect there to be an improvement in Health Literacy domain scores between baseline and 6 weeks after the end of the programme.

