#### 1.3.6 The services where the intervention will be used

The intervention will be used in two very different services.

1. Live Life Better Derbyshire tier 2 weight management services (Public Health, Derbyshire County Council). The aim of the programme is to help people lose weight. The service provides online and face to face group education and advice programmes that run for one session a week over a rolling 12 week period. The programmes have an accompanying website and resources. The

programme is available for all people in Derbyshire. Eight Public Health Improvement Advisors (HIA's) offer advice to groups of up to 25 people who need to lose weight. 33 programmes run across Derbyshire, 19 online and 14 face to face. Attenders are followed up at 12, 26 and 52 weeks and a weight maintenance programme is available.

2. Derbyshire Community Health Service Pulmonary Rehabilitation programme provided within the NHS. The aim of the programme is to improve people's exercise tolerance and respiratory health. This service provides a six week rolling face to face programme that runs across 6 venues in Derbyshire. 15 members of staff, a mixture of physiotherapists, healthcare assistants and specialist nurses, offer supervised exercise and education and advice to people who are limited by their respiratory condition in Derbyshire. The physiotherapists and specialist nurses lead the sessions and have most contact with patients. Up to 12 people attend two sessions a week over the six week period which are a combination of exercise and education.

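### The expected 72 pulmonary rehabilitation participants is the top of the plan's own 48–72 range, with no allowance for the COPD criterion or non-completion and a recruitment window that conflicts with other sections

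*Combined protocol and SAP*

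**What the plan says.** All references are to the combined protocol and SAP.

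- **Section 3.9.2, pulmonary rehabilitation.** Attendance: "Between 8-12 people attend the six week rolling programme across 6 venues". Total: "If we do two cohorts, there will be a minimum of 96 and a maximum of 144 service users", described as "joining the programme between the three month study period in 2024, and who will be invited to take part". A 50% response rate is applied, and two-time-point data are expected "for approximately 72 service users".
- **Section 3.9.2, weight management.** The range is 495–825. The plan then says: "We estimate there will be approximately 660 attendees to the LLBD weight management programme". Applying 50% gives its figure of about 330.
- **Section 3.8.1.** Pulmonary service users must be: "Adults aged 18 or over, with Chronic Obstructive Pulmonary Disease".
- **Section 1.3.6.** The service is described more widely, as being for "people who are limited by their respiratory condition".
- **Section 3.8.2.** Everyone who enters either programme during the study is to be invited, with no mention of diagnosis.
- **Section 3.5.** The second pulmonary assessment is made on completing the programme, at six weeks.
- **Sections 3.8 and 6.** Service-user recruitment is put at a likely six months in section 3.8 and at July to November 2024 in the timetable.

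**The concern.** An expected number should sit near the centre of the range it comes from. Here it sits at the upper limit, although the paragraph just before it takes the centre for the other service. The base counts every joiner, while the eligibility rule appears narrower than the service's intake. The figure is also meant to count people with both assessments, yet it equals the number who would consent at full attendance.

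The CRDQ is the primary outcome for this service, and section 3.9.2 is the only place where its individual-level sample is forecast. If the forecast is too high, the change from baseline to six weeks will be estimated less precisely than the number suggests. Because the recruitment window is stated in three different ways, a reader also cannot tell which sample the study is planning for.

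**Working it through.** **1. Reproduce the plan's figure.** Inputs from section 3.9.2: 8–12 people, 6 venues, 2 cohorts, 50% response.

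- Minimum: 8 × 6 × 2 = 96; 96 × 0.50 = 48
- Midpoint: (96 + 144)/2 = 120; 120 × 0.50 = 60
- Maximum: 12 × 6 × 2 = 144; 144 × 0.50 = 72

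Only the maximum gives 72. To reach 72 from the midpoint, response would have to be 72/120 = 60%. From the minimum it would have to be 72/96 = 75%.

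**2. Compare with weight management.** (495 + 825)/2 = 660, and 660 × 0.50 = 330, as the plan states. The same method gives 60 for pulmonary rehabilitation.

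**3. Recruitment window.** Assume the same throughput per six-week cohort and 50% response, before any reduction for COPD or completion.

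| Cohorts | Minimum | Midpoint | Maximum |
|---|---|---|---|
| 2 (about three months, as in 3.9.2) | 48 | 60 | 72 |
| 3 | 72 | 90 | 108 |
| 4 (about six months, as in 3.8) | 96 | 120 | 144 |

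So 72 is the ceiling for two cohorts and the floor for three.

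**4. COPD share and completion.** The documents give neither. As an illustration only, assume 70–90% have COPD and 70–80% complete. The combined factor runs from 0.7 × 0.7 = 0.49 to 0.9 × 0.8 = 0.72.

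- Two-cohort midpoint: 60 × 0.49 = 29 to 60 × 0.72 = 43 paired scores
- Four-cohort midpoint: 120 × 0.49 = 59 to 120 × 0.72 = 86 paired scores

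Over four cohorts, 72 is still reached if COPD share × completion is at least 72/120 = 60% at the midpoint, 72/96 = 75% at the minimum, or 72/144 = 50% at the maximum.

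**5. Precision.** The 95% confidence interval half-width for a mean change, in units of the SD of change, is t(0.975, n − 1)/√n.

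- n = 72: 0.235
- n = 60: 0.258, about 10% wider than at 72
- n = 48: 0.290, about 24% wider
- n = 36 (within the assumed 29–43): 0.338, about 44% wider

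**The case against.** The strongest reply is that section 3.9.2 is conditional on running two cohorts, and other sections allow longer. A reader might infer from the arithmetic that the study cannot deliver 72. The documents do not support that. With the longer recruitment in sections 3.8 and 6, 72 could be reached even after some loss to the COPD criterion and non-completion. This stands, and it limits the point to the stated two-cohort basis plus the conflict between windows.

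Four further replies:

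- **Ineligible people in the count.** That the 96–144 includes people without COPD is a reasonable inference from section 1.3.6, but no section says how many there are. What the text does show is that sections 1.3.6, 3.8.1 and 3.8.2 do not agree on who is eligible and invited. The 29–43 figure rests on assumed rates.
- **Power.** No power, effect size or precision is stated for 72. Section 3.9.3 already concedes limited power for small differences in the pulmonary service-level comparison over three months. So no stated power claim fails. The half-widths above are an added yardstick; section 3.10.4 plans descriptive analysis and multiple regression.
- **Attrition.** The weight management figure of 330 has no allowance for it either. That is correct, so the omission is not peculiar to this service, but it remains an omission.
- **Comparison with service-level data.** A reader might infer that individual and aggregate results cannot be compared because only the individual data are limited to COPD. That goes too far. Section 3.7 does not say whether the aggregate is restricted by diagnosis. The two analyses also differ by design already: the aggregate includes people who have not consented, and it compares 2023 with 2024.

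**Conclusion.** The point holds on the basis that section 3.9.2 itself states. Two cohorts at 50% response give 48–72 consenting users with a midpoint of 60. The stated 72 is the maximum, and it departs without explanation from the midpoint method used for weight management. This part needs no outside assumption.

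Two further gaps are certain in kind but not in size: there is no reduction for the COPD criterion and none for non-completion before six weeks. The window is also unreconciled across three months, six months and July–November. At the two-cohort midpoint the interval for mean change is about 10% wider than at 72, and at the minimum about 24% wider. Under a longer window the expected number could instead exceed 72.

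The consequence is a favourable forecast for a primary outcome that should be corrected. It does not invalidate the design or any stated power.

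**What to change.** 1. Reconcile the recruitment window across sections 3.8, 3.9.2 and 6, and who is eligible and invited across sections 1.3.6, 3.8.1, 3.8.2 and 3.9.2. Do this first: restating the number on two cohorts alone would leave the conflict in place.
2. Restate the expected number of consenting users as 48–72 (midpoint 60) for two cohorts, or as the matching range for the agreed window. For about four cohorts that is 96–144, with constant throughput stated as an assumption.
3. Apply the service's own COPD share and completion rate to give the expected number of paired CRDQ scores, and state the resulting precision.
4. If the COPD restriction is kept, ask for the aggregate pulmonary data split by COPD where the service can supply it.

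The cost is a revised paragraph, consistent wording in the other sections, two figures from the service and possibly one extra split in the aggregate return. If the two-cohort basis is kept, the stated number becomes less favourable.
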